7.2.2 Serious adverse events (SAEs)

A serious adverse event is any untoward medical occurrence or effect that at any dose:

- results in death;
- is life threatening (at the time of the event);
- requires hospitalisation or prolongation of existing inpatients' hospitalisation;
- results in persistent or significant disability or incapacity;
- is a congenital anomaly or birth defect;
- Any other important medical event that may not result in death, be life threatening, or require hospitalization, may be considered a serious adverse experience when, based upon appropriate medical judgement, the event may jeopardize the subject or may require an intervention to prevent one of the outcomes listed above.

Our proposition will be to only register serious adverse events that have a possible causal relationship with the given food products. Examples of these events include gastrointestinal complaints and allergic reactions, which cause the above mentioned.

7.2.3 Suspected unexpected serious adverse reactions (SUSARs)

Not applicable for this study.

7.3 Follow-up of adverse events

All AEs will be followed until they have abated, or until a stable situation has been reached. Depending on the event, follow-up may require additional tests or medical procedures as indicated, and/or referral to the general physician or a medical specialist. (S)AEs will be reported till the end of study.

8. STATISTICAL ANALYSIS

8.1 Descriptive statistics

Nominal and ordinal variables will be described using frequency tables, modus and medians. Continuous variables will be described in terms of means and confidence intervals or with medians and range, dependent on normality of the data.

Data will be analyzed using IBM SPSS version 22 for descriptive and statistical analyses. All analyses will be performed according to the intention-to-treat principle.

8.2 Primary study parameter

Repeated measures analysis by using mixed models will be performed to evaluate the course over time in quality of life and to analyze the difference between the two groups. The full maximum likelihood estimation will be used to assess the best fit of the model. In these analysis we will adjust for confounders in case of baseline imbalance.

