4.4 Sample size calculation

The sample size calculation is based on the primary outcome of this study: the EORTC-QoL-C30 questionnaire for quality of life. The primary outcome of this study is the difference in quality of life between the 2 groups at the start of the 3rd cycle of chemotherapy. Based on literature, advanced cancer patients with gynecological tumors and tumors of the colon have a mean score of approximately 60 points with a standard deviation of 22 points on the EORTC-QoL-C30 questionnaire. Assuming a difference of 10 points, on a scale of 0-100 points, is a clinically relevant difference in favor of FoodforCare at Home, we estimate that 76 patients are needed in each group in order to obtain a power of 80% (two-tailed t-test, alpha=0.05). Assuming a drop-out rate of 20%, this means a total of 180 patients. In order to improve the power significantly, we will make use of the ANCOVA test [31]. By multiplying the number of patients with $(1-(\rho^2))$ a total of 164 patients will be needed. The correlation between the baseline and follow-up outcome T2 (ρ) is estimated at 0.3.

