8.3 Secondary study parameter(s)

The courses over time and the difference between the groups will also be analyzed for the secondary outcomes. The continuous variables like quality of life of the caregiver, nutritional status (hand grip strength, PG-SGA), nutritional intake and performance scale will be analyzed the same way as the primary outcome. The course over time and the difference between the groups in medication use like anti-emetics e.g. will be treated as a dichotomous outcome (yes/no) and analyzed by using the Chi-square test. The difference in patient satisfaction and severity of symptoms between the two groups will be analyzed using the independent samples t-test.

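### Section 8.2 settles the primary mixed model by best fit, with no candidate models or criterion, and does not carry the cycle-3 comparison of section 4.4 into that model

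*Combined protocol and SAP*

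**What the plan says.** Section 4.4 defines the primary outcome as "the difference in quality of life between the 2 groups at the start of the 3rd cycle of chemotherapy". It sizes the trial for a two-group comparison of that outcome and then reduces the number on the ground that ANCOVA will be used.

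Section 8.2 describes a different analysis. Mixed models are to evaluate the course of quality of life over time and the difference between the groups. On how the model is arrived at, it says: "The full maximum likelihood estimation will be used to assess the best fit of the model". It also provides for adjustment if the groups are imbalanced at baseline. It lists no fixed effects, group-by-visit term, covariance structure, candidate models, fit criterion or contrast, and does not say whether T1 and T2 enter as outcomes or as covariates. Neither the T3 comparison nor the ANCOVA of section 4.4 reappears.

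Section 8.3 states that the continuous secondary outcomes "will be analyzed the same way as the primary outcome".

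Section 3 sets four visits: before chemotherapy (T1, called baseline), at cycle 2 (T2), at cycle 3 (T3) and three months after T3 (T4). The meals run for three weeks between T2 and T3.

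**The concern.** The meals can affect only T3 and, if the benefit lasts, T4. In a model with four visits as outcomes, the T3 effect is therefore carried by the group-by-visit term. Full maximum likelihood, unlike REML, allows models with different mean terms to be compared. An analyst who judged fit in this way, found that the group-by-visit term did not improve it and left it out would still be following section 8.2.

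What would then be reported is one group difference averaged over the visits in the model. That is not the quantity in section 4.4, and under most model forms it is much smaller. Its size would also depend on which fit criterion was chosen, which the plan leaves open. Section 8.3 extends the same freedom to the continuous secondary outcomes.

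**Working it through.** **The plan's own figure.** Section 4.4 assumes "a mean score of approximately 60 points with a standard deviation of 22 points" and a 10-point difference. The normal-approximation formula gives n = 2 × (1.96 + 0.84)² × (22/10)² ≈ 76 per group, matching "76 patients are needed in each group". The last step also reproduces: 180 × (1 − 0.3²) = 163.8, so 164. (The step from 152 to 180 is not the usual inflation, since 152/0.8 = 190. That is a separate matter; 164 is used here.)

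**Inputs from the plan.** 164 × 0.8 = 131.2 evaluable, or m = 65.6 per group; SD 22 (variance 484); 10 points at T3; correlation 0.3. Section 4.4 attaches the 0.3 to baseline and a follow-up labelled T2.

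**Assumptions.** The same correlation ρ between all pairs of visits (compound symmetry); ρ of 0.5 and 0.7 as alternatives; no effect at T1, T2 or T4 unless stated; all four visits as outcomes unless stated.

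**Fixed T3 comparison.** SE = 22 × √(0.91 × 2/65.6) = 3.66. 10/3.66 = 2.73, and Φ(2.73 − 1.96) ≈ 0.78. Power is about 78% at ρ = 0.3.

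**Effect left if group-by-visit is dropped.** The common group effect is (1′V⁻¹d)/(1′V⁻¹1), where d holds the visit-specific differences and V is the covariance matrix. Under compound symmetry the visits are weighted equally:

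- four visits as outcomes: (0 + 0 + 10 + 0)/4 = 2.5 points
- T1 as covariate: (0 + 10 + 0)/3 = 3.3 points
- T1 and T2 as covariates: (10 + 0)/2 = 5.0 points
- four visits, 5 points persisting at T4: 15/4 = 3.75 points
- four visits, all 10 points persisting at T4: 20/4 = 5.0 points

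With four visits, AR(1) correlation and a T3-only effect, the result is 2.1, 1.7 and 1.2 points at ρ = 0.3, 0.5 and 0.7. AR(1) does not lower it in every form: with T1 and T2 as covariates it gives 5.3, 6.0 and 7.25 points.

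For the 2.5-point case at ρ = 0.3, the variance of a four-visit mean is 484 × (1 + 3 × 0.3)/4 = 229.9. SE = √(2 × 229.9/65.6) = 2.65, and power is about 16%.

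**How often the term would be dropped.** The departures from the common effect are (−2.5, −2.5, 7.5, −2.5), with sum of squares 75. The non-centrality is λ = (m/2) × 75/[484(1 − ρ)] = 2460/[484(1 − ρ)]. The term is dropped when a non-central chi-square on 3 df falls below 7.81 (likelihood ratio test at 5%), 6 (AIC) or 3 × ln 131 = 14.63 (BIC).

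| ρ | λ | Likelihood ratio | AIC | BIC |
|---|---|---|---|---|
| 0.3 | 7.26 | 39% | 26% | 79% |
| 0.5 | 10.17 | 23% | 14% | 64% |
| 0.7 | 16.94 | 5% | 2% | 29% |

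If 164 patients were evaluable, λ at ρ = 0.3 would be 41 × 75/338.8 = 9.08, and the term would be dropped in about 28% (likelihood ratio) or 17% (AIC) of trials.

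**Selection followed by testing.** Simulation with 131 patients used correlations of 0.3 throughout or between 0.25 and 0.5, and 0 or 5 points at T4. Overall power was about 63 to 68% (likelihood ratio), 70 to 73% (AIC) or 24 to 43% (BIC), against 76 to 78% for the fixed T3 comparison. With no true effect, the error rate was about 6 to 8% with likelihood ratio or AIC.

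**The case against.** The strongest reply is that the best-fit sentence may be about the covariance structure alone. Section 8.2 never mentions a group-by-visit term or its removal, and maximum likelihood can also compare covariance structures. On that reading little is lost: choosing among three structures by BIC gave error rates of 3.5 to 6.2% in simulation, against 4.8 to 5.3% for an unstructured REML fit. Full maximum likelihood in place of REML makes standard errors only about 1% too small. This stands as a possible reading, but the sentence does not limit itself to it.

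A second reply is that section 4.4 already names T3, so a model that cannot estimate the T3 difference is not admissible. That is a fair reading of the intention. Section 8.2 does not say so, and the remedy is to write it there.

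Third, the drop rates depend on choices the documents do not make. No criterion is named, the worst figures belong to BIC, and higher correlations reduce all the rates sharply. Section 6.5 plans extra inclusions to offset withdrawals, so 131 evaluable patients may be too few. All of this stands, and it is why the figures are illustrations.

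A reader might infer that the model will be chosen on unblinded data. Section 6.3 says that patients know their group and that the coordinating researcher cannot be blinded; it is silent on the analyst. A reader might also infer that the effect will be diluted to a quarter. That needs four visits as outcomes, equal weights and an effect at T3 only.

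**Conclusion.** The concern holds as a gap between two sections. Section 4.4 fixes a T3 difference as the primary outcome, and section 8.2 leaves the model to a fit rule that does not protect it. The documents do not say that the group-by-visit term will be dropped; they allow it.

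Under the stated assumptions the chance of dropping runs from 2% (AIC, ρ = 0.7) to 79% (BIC, ρ = 0.3). With a T3-only effect and compound symmetry, the remaining estimate is 2.5 to 5 of 10 points, depending on whether T1 and T2 are covariates. It is lower under AR(1) with four visits as outcomes, and higher if the effect persists at T4. Only the 0.3 correlation, the SD, the 10 points and the 20% drop-out come from the plan. This should be corrected before the data are analysed, because a fixed T3 comparison avoids the problem with the same software.

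**What to change.** Rewrite the model paragraph of section 8.2 so that the mean structure is not selected by fit:

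- visit enters as a factor, and group-by-visit is always kept, whatever its p-value or any information criterion;
- the baseline value is adjusted for, as section 4.4 assumes, and the paragraph says whether T2 is an outcome or a covariate;
- the primary test is the group difference at T3 from this model;
- any fit comparison is limited to the covariance structure under a named criterion, or one structure is named with an ordered list of fallbacks if it does not converge.

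REML for the final estimates and tests is a minor refinement. Section 8.3 should refer to the same fixed model for the continuous secondary outcomes.

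The cost is one paragraph. The downside is a few more parameters and less freedom to simplify the model after the data are seen.

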3. STUDY DESIGN

A randomized controlled trial will be performed in palliative abdominal oncology patients at home. Inclusion will take place at the department of Medical Oncology at the start of palliative chemotherapy. The study is intended to be performed from March 2017 to July 2018. Patients will be randomly assigned to one of two groups before the start of the second cycle of chemotherapy because it is expected that FoodforCare at Home will make the largest difference during this cycle. The intervention group will receive meals from FoodforCare at Home and the control group will continue their regular diet for three weeks from the second cycle of chemotherapy until the next cycle of chemotherapy. Before the start of this study, a pilot study will be performed to determine whether the intervention is feasible in terms of logistics and delivery of the meals for example.

Measurements will take place at four time points during the study period i.e. before the start of chemotherapy, at the 2nd cycle of chemotherapy, at the 3rd cycle of chemotherapy and three month after T3 (figure 1). These measurements will be performed by AYA's/research assistants who will visit the patients at home. Time point 1, before the start of chemotherapy, will serve as the baseline measurement. At this moment, informed consent will be obtained and signed by the patient and the MUST score will be determined. Quality of life of patient and caregiver, nutritional intake, nutritional status, functional status and medication use will be assessed at all time points. For quality of life, the EORTC-QoL-C30 questionnaire will be filled in by the patients and the Caregiver Reaction Assessment by their caregivers. Nutritional status will be assessed using the handgrip strength measurement, the PG-SGA and performance scale by means of the Karnofsky score and the SPPB. Data on nutritional intake will be recorded using a 3-day food diary, which the patients will fill in by themselves. Medication use will be obtained from the patient's medical file. Additionally, during the intervention period, patients will record their symptoms using 'Utrecht Symptoom Dagboek' and medication use will be assessed by using a diary. At time point 3, patient satisfaction in the intervention group will be assessed by the Net Promoter Score with additional questions. An overview of the measurements can be found in table 1.

Figure 1. Flowchart of the study design of the FoodforCare at Home study.

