6.3 Randomisation, blinding and treatment allocation

Patients will be randomized into two groups at the department of medical oncology in the Radboudumc. This will be performed by using the randomization program which is part of the clinical data management system 'Research Manager'. This validated web based data management system will be used during the entire study. The researcher will have a password to the randomization program. After randomization, a study number will be assigned to the patient. The researcher documents the patient information and study number in a designated source document. The study number and birth date will be listed on all study documents. The randomization will be stratified on tumor type and type of chemotherapy because of the possible effect on the primary outcome. This stratification reduces the risk of an uneven distribution of prognostic factors. We will not stratify for other characteristics; the exclusion criteria will contribute sufficiently to a homogenous patient population.

Blinding is not possible for the coordinating researcher, since one group will receive FoodforCare at Home and the other group will receive no additional products. Patients have to be aware of in which group they are in. Whether blinding is possible for the AYA's/

research assistants will be examined during the pilot study. In that case, patients will be asked not to tell the AYA's/research assistants in which group they are allocated.

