6.5 Replacement of individual subjects after withdrawal

During the inclusion period, additional patients will be included to be able to achieve the necessary number of patients in case of withdrawal of patients during the study.

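### Section 8.2 does not carry over the baseline-adjusted cycle-3 comparison that sized the trial in 4.4, and ties covariate adjustment to observed baseline imbalance

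*Combined protocol and SAP*

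**What the plan says.** Section 4.4 of the combined protocol and SAP defines the primary outcome as the "difference in quality of life between the 2 groups at the start of the 3rd cycle of chemotherapy". It starts from 76 patients per group (SD 22, difference 10, two-sided alpha 0.05, power 80%), allows for 20% drop-out to reach 180, and then states: "In order to improve the power significantly, we will make use of the ANCOVA test". Multiplying by one minus the squared correlation, with the correlation taken as 0.3, it concludes that "a total of 164 patients will be needed". It labels the follow-up outcome in that correlation T2.

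Section 3 lists four measurement times and fixes the baseline: "Time point 1, before the start of chemotherapy, will serve as the baseline measurement". In that numbering the start of cycle 3 is T3, not T2.

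Section 8.2, the primary analysis, reads differently: "Repeated measures analysis by using mixed models will be performed to evaluate the course over time in quality of life", and also to analyse the difference between the groups, with full maximum likelihood. Its only rule on covariates is "In these analysis we will adjust for confounders in case of baseline imbalance". It mentions neither ANCOVA nor a time point, and does not say how baseline QoL enters.

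Section 6.3 states: "The randomization will be stratified on tumor type and type of chemotherapy because of the possible effect on the primary outcome". Section 8.2 does not name these two factors as model terms. Section 6.5 says that "additional patients will be included to be able to achieve the necessary number of patients in case of withdrawal".

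**The concern.** The reduction from 180 to 164 is bought by baseline adjustment at one time point. The section that governs the primary analysis does not commit to that adjustment or to that time point. A mixed model can deliver both, but only in some of its forms. If T1 is one of the repeated outcomes and each group has its own T1 mean, the T3 contrast in complete data is simply the raw T3 difference, and the saving is not earned.

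The imbalance rule adds a second problem. It lets the observed data decide which covariates enter the primary model, without saying how imbalance is judged or which variables are candidates. Imbalance is also a poor criterion, since what a covariate is worth depends on how strongly it predicts the outcome. Tumour type and chemotherapy type will usually look balanced because the randomisation is stratified on them. The rule therefore tends to leave out the two factors that the protocol itself says may affect the primary outcome.

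At stake are a few points of power, and a primary result with two defensible versions, adjusted and unadjusted, available after the data are seen.

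**Working it through.** **Inputs from 4.4:** difference 10, SD 22, two-sided alpha 0.05, power 80%, drop-out 20%, correlation ρ = 0.3, total 164. The stated 180 is taken as given.

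**The plan's own figures.**
- Per group, normal approximation: 2 × [(1.960 + 0.842) × 22 / 10]² = 76. This reproduces.
- ANCOVA step: 180 × (1 − 0.3²) = 180 × 0.91 = 163.8, so 164. This reproduces, and it shows that the 16 patients saved depend on baseline adjustment alone.

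**T3 power with and without baseline QoL** (noncentral t). The standard error is 22 × √(2/n) unadjusted and 22 × √(1 − ρ²) × √(2/n) adjusted.

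*None replaced:* 164 × 0.8 = 131.2, so n = 65.6 per arm.
- Unadjusted, patients with T3 only: SE 3.84, power 73.4%.
- Adjusted for T1: SE 3.66, power 77.3%.
- Likelihood model with free T1 means, using T1 from patients later lost (T1 on 82 per arm, T3 on 65.6): SE = √{2 × 484 × [0.91/65.6 + 0.09/82]} = 3.81, power 74.1%.
- Loss: 77.3 − 73.4 = 3.9 points, or 77.3 − 74.1 = 3.2 points.

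*Withdrawals replaced up to 164 evaluable (one reading of 6.5):* n = 82 per arm.
- Unadjusted 82.5%, adjusted 85.8%, a loss of about 3 points.

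**Sensitivity to ρ** (adjusted power, and loss against the unadjusted 73.4% or 82.5%):

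| ρ | 65.6 per arm | Loss | 82 per arm | Loss |
|---|---|---|---|---|
| 0.1 | 73.8% | 0.4 | 82.8% | 0.3 |
| 0.3 | 77.3% | 3.9 | 85.8% | 3.3 |
| 0.5 | 84.7% | 11.3 | 91.6% | 9.1 |

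At ρ = 0.5 and 65.6 per arm, the loss is about 9 points rather than 11 if the likelihood model uses T1 from drop-outs.

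**The imbalance rule.** Section 8.2 gives no trigger, so three were assumed: adjust for T1 QoL only if a baseline t-test has p below 0.05, 0.10 or 0.20. This also assumes that baseline QoL counts as a confounder. Results are from 100,000 simulated trials, 66 per arm, ρ = 0.3, normal data.

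| Rule | Power | Type I error |
|---|---|---|
| Never adjust | 73.4% | about 5% |
| Adjust if p < 0.05 | 73.7% | 4.7% |
| Adjust if p < 0.10 | 73.9% | 4.6% |
| Adjust if p < 0.20 | 74.4% | 4.5% |
| Always adjust | 77.0% | about 5% |

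A fixed trigger is slightly conservative and recovers at most about 1 of the 4 points.

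With the trigger left open, the adjusted and unadjusted T3 tests disagree on significance in 8.4% of trials when the effect is 10 points, and in 2.7% when there is none. If whichever is significant were reported, type I error would be (4.90% + 4.98% + 2.70%) / 2 = 6.3%.

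**Stratification factors.** Leaving out prognostic stratification factors makes the standard error too large. The documents give no prognostic strength, so this loss cannot be computed. The price of including them is small: with the arms balanced on the factors, 1 to 10 extra degrees of freedom move T3 power at 65.6 per arm from 77.3% to 77.2%.

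**The case against.** The strongest reply is that the protocol does commit to T3 and to ANCOVA, in 4.4. That stands. A reader might infer that the primary time point and method are fixed nowhere, and the documents do not support that. The defect is that 8.2 describes another analysis without reconciling it with 4.4, so it is unclear which section governs.

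Second, a mixed model can use baseline QoL fully, and 8.2 does not exclude this. Also true: the gap is a missing commitment, not a wrong model. Even the free-means form draws some information from T1 in patients lost later, which brings the loss nearer 3 points than 4. Section 6.6, however, speaks only of using data from patients who withdraw after time point 3. If earlier withdrawals are left out, the 73.4% figure applies.

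Third, the effect is small, and under the replacement reading of 6.5 both figures exceed 80%. This stands too, and it limits the point.

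Fourth, the confounders in 8.2 may mean patient characteristics rather than baseline QoL, which is itself one of the repeated measurements. The simulated triggers would then be less relevant. But the rule would give baseline QoL no role at all, and the covariate list would still be open.

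**Conclusion.** The point holds as a mismatch between 4.4 and 8.2 that should be fixed. It is not a fatal flaw. At ρ = 0.3 the cost of not using baseline QoL is about 3 to 4 points of T3 power with 164 randomised, 20% lost and none replaced, and about 3 points with 164 evaluable. Only these differences belong to this point, not the level of 77% itself. The figures assume a single QoL score, SD 22, a 10-point effect and the plan's own correlation. The loss grows or shrinks with that correlation, as tabulated.

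Two stronger readings go too far. One is that the mismatch leaves the trial underpowered: if 6.5 means replacement up to 164 evaluable patients, power exceeds 80% with or without adjustment. The other is that the imbalance rule inflates type I error: a fixed trigger is slightly conservative. The 6.3% arises only if the more favourable of two results is reported, which the plan does not propose. What the documents do support is that the open rule leaves room for that choice after the data are seen, in a trial whose coordinating researcher is not blinded (6.3).

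**What to change.** In 8.2:
- State that the primary test is the group difference in QoL at T3 (start of cycle 3), estimated from the mixed model.
- State that baseline (T1) QoL is always used, either as a covariate or with the T1 group means constrained equal, and that tumour type and chemotherapy type are always in the model.
- Delete the sentence on adjustment in case of baseline imbalance.
- Report T4 and the course over time as secondary.

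In 4.4, align the T2 label on the follow-up outcome with the T1 to T4 numbering of section 3.

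The cost is wording only. T1 QoL is already collected, and both stratification factors are already recorded for randomisation. No patients, visits or data are added, and the extra model terms cost less than 0.1 point of power if the arms stay balanced on them.
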